## 16. Version History

Version	Summary of Changes	Author(s)/Title
1.0	new issue	[name] Clinical study manager, Neurolief
2.0	Updated inclusion/exclusion criteria, secondary and exploratory endpoints, adding an OLE stage and study flow. added the central trainer role and the sites raters training.	[name] Clinical study manager, Neurolief
3.0	
 
updated inclusion/exclusion criteria,
 
updated assessment of safety (section 9.9)
 
the length of the DB and OL treatments stages were prolonged to 8 weeks each. Updated “Expected treatment time for total DB phase” as a result of DB period time extension
 
Re-evaluation of the assigned treatment regimens according to the subjects’ MDD assessment was added to visit 5 procedures
 
Up to 36 additional subjects ages 18-21 are added to the study overall sample size. Analyses sets and statistical analysis sections update accordingly.
 
Updated sections 9.9, 9.12 & 10.1 to withdraw subjects with a “yes” answer to c-SSRS Q4 and Q5
 
Device and dedicated app SW versions updated to support users with IOS12 and above.
 
Updated maximum sample size upon IA results to 250 (instead of 200) and the respective IA decision rules.
 
	[name] Clinical study manager, Neurolief

## 17. Appendixes

ISO	International Organization of Standardization
ITT	Intent to Treat
LTFU	Lost To Follow Up
MDD	Major Depressive Disorder
MDRS/MADRS	Montgomery-Asberg Depression Rating Score
mITT	modified Intent to Treat
mYITT	Modified Young Intent to Treat
NTF	Note To File
PP	Per Protocol
QIDS	Quick Inventory of Depressive Symptomatology
Q-LES-Q	Quality of Life Enjoyment and Satisfaction Questionnaire
RDC	Remote Data Capture
SAP	Statistical Analysis Plan

1. INTRODUCTION

This Statistical Analysis Plan (SAP) is a more detailed companion to the Statistical Methods section of the study titled “The MOOD study – external Combined Occipital and Trigeminal Nerve Stimulation (eCOT-NS) for the treatment of Major Depressive Disorder (MDD)” and provides a comprehensive description of the analysis sets, endpoints, methods, and data analyses to be used. This SAP prevails when differences exist in descriptions or explanations provided in the protocol and the SAP. We shall address analysis strategies for the open label stage of the study. Addressed as well is a plan for prognostic factor analysis to identify potential baseline parameters related to the primary endpoint and its derivatives.

Relivion®DP, an external Combined Occipital and Trigeminal Afferent Stimulation (eCOT-AS) is proposed as a novel treatment for MDD. The combination of neuromodulation of both the occipital and the trigeminal nerve branches non-invasively is made possible for the first time, after having been successfully performed either separately or in invasive procedures.

Major depressive disorder is one of the leading causes of disability worldwide. However, treatment options are still limited, therefore new approaches are needed to enhance clinical improvement. The non-invasive combined neuromodulation of both the occipital and trigeminal nerve branches is a safe, self-administered novel technology with high potential for treating MDD patients. Based on this rationale, Neurorelief developed the Relivion®DP, a neuro-stimulator applying combined occipital and trigeminal afferent stimulation for treatment of major depressive disorder (MDD). Following completion of an early clinical study showing promising results, Neurorelief designed the proposed clinical trial to evaluate the safety and efficacy of the Relivion®DP in a two-arms controlled, double blinded randomized study.

The MOOD Study will evaluate the safety and efficacy of a self-administered treatment for MDD using an external combined occipital and trigeminal afferent stimulator (Relivion®DP).

This pivotal clinical investigation is intended to support future marketing applications (US FDA and CE) for Neurorelief’s Relivion®DP device.

2. STUDY DESIGN AND OBJECTIVE

2.1 Study Objectives

The main objective of the study is to evaluate the safety and efficacy of a self-administered treatment for MDD using an external combined occipital and trigeminal nerve stimulator (Relivion®DP). This pivotal clinical investigation is intended to support future marketing applications (US FDA and CE) for Neurolief's Relivion®DP device.

2.2 Study Design

2.2.1 Experimental Design

This is a prospective, randomized, double-blind, parallel-group, sham controlled, multi-center clinical investigation followed by an active open label extension period. All enrolled patients are those treated with the Relivion®DP device either by active treatment or sham treatment. The treatment will be done according to the IFU. Patients' duration in the study will be up to 20 weeks (including the screening period).

In this study for the double-blind phase, the Relivion®DP was provided in therapeutic and non-therapeutic modes, for the Active and Sham groups respectively:

- Active Treatment: For the therapeutic mode the device will be preset to the following parameters: stimulation waveform- symmetrical biphasic, phase duration 130-300 microseconds, pulse frequency 80Hz, trigeminal stimulation intensity – up to 6.7mA, Occipital stimulation intensity– up to 18mA.
- Sham Control: For the non-therapeutic mode the device will be preset to the following parameters: Stimulation waveform- symmetrical biphasic, phase duration 100 microseconds, pulse frequency 0.33 Hz, trigeminal stimulation intensity up to 5mA, occipital stimulation

intensity up to 10mA for 3 minutes, then gradually decrease to 0.2 mA and stays constant throughout the remaining treatment duration.

Both Active and Sham stimulation devices are packaged and labeled identically to maintain blinding of both the subject and study staff.

The double blind Relivion®DP treatment will last 60±20 minutes (preferably in two equal sessions of 30±10 minutes each) per day for 5-7 days a week (intensity level up to 50) for a period of 8±1 weeks.

For purposes of the active open label phase, only active treatments were applied. Open label phase treatment regimens would be as follows, according to the subject HDRS score at the end of the double-blind phase, for a period of 8±1 weeks:

Maintenance treatment (for HDRS remitter subjects): 40±10 minutes 3-4 times a week (intensity level up to 50).

Daily treatment (for HDRS responder subjects): 5-7 days a week 60±20 minutes per day (preferably in two equal sessions of 30±10 minutes each).

An interim analysis was performed after 86 (~80% of the calculated sample size) evaluable subjects were accrued, mainly for sample size re-assessment. The primary, as well as the safety endpoints were assessed in the ITT, mITT, PP and mYITT analysis sets. The interim analysis indicated “Favorable” results, therefore the Data Safety Monitoring committee (DMC) issued their formal recommendation that the study should continue enrollment with the original planned sample size of 124, without the need to increase the sample size.

2.2.2 Planned Sample Size and Study Hypothesis

The initial planned sample size was a total of 124 subjects, aged 22-70, randomized into two treatment arms, active Relivion®DP, and sham.

An additional up to 36 subjects (30+15% dropout) were planned to be randomized in the age range 18-21, to assess efficacy in this age range as well.

In this study, we will test the following hypotheses:

- $H_0: M_R = M_S$
- $H_1: M_R \neq M_S$

Where M_R and M_S represent the mean change from baseline in HDRS17 total score to week 8 in subjects suffering from MDD in the active treatment group and sham group, respectively

3. DATA MANAGEMENT

All data will be collected using a paper CRF and/or Remote Electronic Data Collection (RDC/EDC) system. The clinical sites will use hard copy and/or electronic case report forms (eCRFs) to document the information required by the study protocol.

The EDC allows for the secure collection, transmission, validation, monitoring and real-time administration of study data gathered at investigative sites. The system allows password-restricted access to clinical trial information based on individuals' roles and responsibilities. The EDC are compliant with 21 CFR Part 11 and FDA's "Guidance: Computerized Systems Used in Clinical Trials".

Data reported on the CRF/eCRF should be driven from source documents (Section 14.5 in the study protocol) and be consistent with these source documents. Editing of data is done under full audit trail. Paper CRF worksheets may be provided to the investigational site to assist with data collection for the required fields.

Required data will be recorded on CRF/eCRFs by authorized site personnel as indicated on the Delegation of Authority Log. The Investigator will ensure that all eCRFs are completed promptly, completely, and accurately. Information on case report forms must conform to the information in the source documents.

The Sponsor will oversee and/or perform all data management functions. Data management functions include database development, system maintenance, data queries, and report generation.

Investigators must ensure that clinical records clearly indicate that the subject has been enrolled in a clinical investigation. Regulations require that Investigators maintain information in the study subject's medical records to corroborate data collected on the CRF/eCRF. In order to comply with these regulatory requirements, the study site will manage the following information, and

retain/manage it as required to make it available to monitors, auditors and/or regulatory bodies. Complete hospital and clinical medical records for all study subjects should include all study required procedures, labs and assessments as noted in Study schedule and Site Collection Data.

4. STATISTICAL SOFTWARE

All statistical analyses and data presentations, including tabulations and listings, will be performed using the SAS version 9.4 (SAS Institute, Cary NC, USA) software.

5. SAS® PROGRAMS VALIDATION

All SAS® programs used for analyses described in this document will be validated by double programming **or** code review before the final analysis as per BioStats SOP's.

6. RANDOMIZATION AND BLINDING

Up to the date of the finalization of this SAP the treatment code was not revealed. Subjects will be prospectively randomized into the clinical study. Randomization will occur only after the subject provides informed consent, completes all required screening and baseline procedures, and satisfies the study eligibility criteria. Eligible subjects will be randomly allocated (with a 1:1 ratio) to one of the following 2 treatment groups based on a randomization scheme using the permuted block method stratified by center:

- Active stimulation.
- Sham stimulation.

The Relivion®DP Active and Sham devices will look the same and will be provided in the same packaging bearing the same labeling. Hence, both subjects and study personnel will remain blinded to the assigned treatment group. Furthermore, the sponsor, investigator, MDD assessor and device trainer are all blinded to the treatment assignment.

7. MISSING DATA HANDLING & SENSITIVITY ANALYSES

The study outcomes will not be evaluated for patients who drop out prior to randomization. The primary endpoint will be analyzed using a repeated measures ANCOVA model which can handle data missing at random and we do not expect a high proportion of dropouts until the primary endpoint is measured. Therefore, for this evaluation no imputation of missing data is considered beyond the model estimates. Additionally, imputation of data such as by LOCF may harm linearity in such models, therefore, for this evaluation no imputation of missing data is considered beyond the model estimates.

Nevertheless, a sensitivity analysis based upon last observed values (LOV) may be performed. The Last Observed Value (LOV) is defined as the last available post baseline visit data up to and including the last treatment visit or termination visit. For categorical variables (such as response and remission rates at week 8) the LOCF concept will be applied. Baseline characteristics of patients who drop out will be evaluated by study group to evaluate the potential reason for differential drop out if needed.

The primary endpoint analysis, using the same methods described, will also be performed on the PP and ITT analysis sets as sensitivity analyses.

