### **9.1.4. Visit 3 – 4 weeks Follow up (Day 28±7)**

Written below are the assessments to be completed at Visit 3 (either on site or remotely):

- Depression symptoms questionnaires:

- By site qualified rater: HDRS21 (HDRS17- removing 4 last questions from the HDRS21), MDRS, CGI-S & CGI-I
- By subject: QIDS-SR-16. Subject self-reported questionnaire may be filled in electronically (ePRO) or by hard copy.
- Suicidal intent assessment by the investigator team (C-SSRS)
- Change in concomitant medications, if any.
- Significant change in health status, if any.
- Adverse events will be documented.

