## 9.12. **Subject Withdrawal or Discontinuation**

The reason for study exit, including screen failure, will be documented on the applicable CRF/eCRF and in the subject file. The Sponsor must be informed of each withdrawal case.

Once a subject has been enrolled in the study, he/she may withdraw his/her consent to participate in the study at any time without prejudice. Participation in this clinical investigation is entirely voluntary.

In the event the subject withdraws consent during the study, the date of withdrawal will be documented. Individual subjects will not be replaced.

 Neurolief Brain Innovation	MOOD: CLINICAL INVESTIGATION PLAN	Doc No.: CL-CIP-201 Rev: REV.3 / 09June2021 Pg. 58 of 92
--	--	--

The investigator may prematurely discontinue the participation of any subject in the study.

If the Investigator voluntarily removes a subject from further study participation, supporting documentation must be in place for the rationale and date of removal. The Investigator may withdraw a subject from the study at any time for the following reasons:

- Severe side effects clearly related to the study procedures.
- Presence or appearance of exclusion criteria
- Clinically significant current suicidal intent as assessed by the investigator team: a "yes" answer to Q4 or Q5 on C-SSRS questionnaire.
- Appearance of accompanying diseases rendering further participation in the study impossible
- A significant protocol deviation, as determined either by the Sponsor or the Investigator.
- Subject noncompliant with procedures
- Subject noncompliant with visits
- At the specific reasonable request of the Investigator

Attempts will be made to conduct an exit/final visit prior to a subject terminating participation in the study. The reason for early discontinuation will be documented in the source documents and eCRF. Data collected up to the point of withdrawal or premature discontinuation will be included in the data analysis, unless specifically requested not to.

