#### 12.2.2. Secondary and exploratory endpoint variables

The secondary endpoints of responder and remission will be represented in the form of binary variables which will be assigned the value of "1" if the subject is a "responder" or a "remitter" per specific secondary endpoint, and "0" otherwise. Other exploratory binary endpoints will be defined in a similar manner.

Secondary and exploratory endpoints described as changes from baseline, such as QIDS-SR-16, CGI-S and CGI-I and MDRS will be calculated by subtracting the subject's baseline score from the score at each visit.

 Neurolief Brain Innovation	MOOD: CLINICAL INVESTIGATION PLAN	Doc No.: CL-CIP-201 Rev: REV.3 / 09June2021 Pg. 70 of 92
--	--	--

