### 12.9.5. Handling of Missing Data

The study outcome will not be evaluated for patients who drop out prior to randomization. The primary endpoint will be analyzed using a repeated measures ANCOVA model which can handle data missing at random and we do not expect a high proportion of dropouts until the primary endpoint is measured. Therefore, for this evaluation no imputation of missing data is considered beyond the model estimates. Additionally, imputation of data such as by LOCF may harm linearity in such models, therefore, for this evaluation no imputation of missing data is considered beyond the model estimates. Nevertheless, a sensitivity analysis based upon last observed values (LOV) may be performed. The Last Observed Value (LOV) is defined as the last available post baseline visit data up to and including the last treatment visit or termination visit.

For categorical variables (such as response and remission rates at week 8) the LOCF concept will be applied.

 Neurolief Brain Innovation	MOOD: CLINICAL INVESTIGATION PLAN	Doc No.: CL-CIP-201 Rev: REV.3 / 09June2021 Pg. 79 of 92
--	--	--

Baseline characteristics of patients who drop out will be evaluated by study group to evaluate the potential reason for differential drop out.

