8.2 Secondary Efficacy Endpoints

Secondary efficacy endpoints include:

- **Proportion of responder subjects** - defined as the percent of subjects achieving at least 50% reduction from baseline in their HDRS-17 total score, 8 weeks post Relivion®DP treatment initiation.

- **Proportion of subjects achieving remission** - defined as the percent of subjects with HDRS-17 score≤7 at 8 weeks post Relivion®DP treatment initiation.
- **Change from baseline** to week-8 post Relivion®DP treatment initiation **in depressive symptoms** as measured by **MADRS** total score.

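### Week-8 response and remission rest on last observation carried forward alone, so a leaver whose last HDRS-17 met the criterion counts as a week-8 success

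*SAP*

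**What the plan says.** Response and remission are two of the three secondary endpoints. They are tested only if the primary endpoint succeeds, with Benjamini–Hochberg adjustment (SAP 9.2). SAP 8.2 fixes response at week 8: "defined as the percent of subjects achieving at least 50% reduction from baseline in their HDRS-17 total score, 8 weeks post" treatment start. Remission is an HDRS-17 of 7 or less at the same time.

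For missing values, SAP section 7 states: "For categorical variables (such as response and remission rates at week 8) the LOCF concept will be applied". Protocol 12.9.5 carries the same sentence.

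For the continuous HDRS-17, both documents rely on the repeated-measures model and missing at random. They use no further imputation because "imputation of data such as by LOCF may harm linearity in such models". A last-value analysis of the primary endpoint is left optional: "a sensitivity analysis based upon last observed values (LOV) may be performed".

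Protocol 12.2.2 says that the binary endpoints are "represented in the form of binary variables which will be assigned the value of" 1 for a responder or remitter and 0 otherwise. It does not mention missing values.

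Between baseline and week 8 the only scheduled HDRS is at Visit 3 (day 28±7). Protocol 9.12 adds: "Attempts will be made to conduct an exit/final visit prior to a subject terminating participation in the study".

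**The concern.** Response and remission are cut-points of HDRS-17, so a missing week-8 rating is the same missing datum in the primary and the secondary analysis. In the primary model it is handled under missing at random. In the secondary analysis it is frozen at the last value, usually week 4.

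The plan does not expect a flat course. The feasibility means in protocol 12.4 go from -5.95 at week 3 to -8.4 at week 6. A carried value therefore gives neither the score the subject would probably have reached by week 8 nor a plain record that the subject left.

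Three things are at stake:
- A subject who met the criterion early and then left for any reason is reported as a week-8 success.
- No sensitivity analysis of this rule is specified, so its influence on a tested secondary endpoint would not be visible.
- A subject with no post-baseline HDRS has nothing to carry, and the denominator is not stated.

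**Working it through.** **1. The plan's own size.** With a difference of 3.3 and SD 6 (protocol 12.4), d = 3.3/6 = 0.55. The two-sample t-test needs 52.87, so 53 per arm, with power 80.1%. This reproduces the plan. 106/0.85 = 124.7, against 124 stated. With 62 randomised per arm, 15% drop-out is 0.15 × 62 = 9.3 subjects per arm, and one subject is 1/62 = 1.6 points.

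**2. What the rule changes.** Let d be an arm's share of subjects with a carried value and q the share of those who met the criterion at their last rating. On the same denominator, LOCF minus missing = non-responder shifts the treatment difference by

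d_A × q_A − d_S × q_S.

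**3. Size with equal, random drop-out (ITT, 62 per arm).**
- From the protocol: 15% drop-out; week-3 mean changes -5.95 (active) and -3.45 (sham), SD rounded to 5, used here for week 4. The sham figure is derived there from d = 0.5, not observed.
- Assumed: baseline 21.5 (SD 3.5), independent of change; week-8 changes -8.7 and -5.4 (the planned 3.3-point difference), SD 6; two thirds of drop-out after Visit 3, so d = 0.10 (6.2 subjects) and 5% (3.1) with nothing to carry.

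A reduction of at least half the baseline has probability Φ((m − 10.75)/√(SD² + 0.25 × 3.5²)), where m is the mean reduction.
- Week 4: active Φ((5.95 − 10.75)/5.30) = 0.182; sham Φ((3.45 − 10.75)/5.30) = 0.084. Credited leavers: 6.2 × 0.182 = 1.1 and 6.2 × 0.084 = 0.5.
- Week 8: active Φ((8.7 − 10.75)/6.25) = 0.371; sham Φ((5.4 − 10.75)/6.25) = 0.196.

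| Rule | Active | Sham | Difference |
|---|---|---|---|
| Missing = non-responder (0.85 × week-8 rate) | 31.6% | 16.7% | 14.9 |
| LOCF, all 62 in denominator (add 0.10 × q) | 33.4% | 17.5% | 15.9 |
| LOCF, subjects with nothing to carry omitted (divide by 0.95) | 35.2% | 18.4% | 16.7 |
| Missing at random (week-8 rate) | 37.1% | 19.6% | 17.5 |

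The shift from LOCF is 0.10 × (0.182 − 0.084) = 0.0098, about 1 point. Simulation with a correlation of 0.6 between visits gave 33.3% against 31.5% (active) and 17.4% against 16.6% (sham).

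**4. Size with unequal drop-out or early response.** Assumed completer response is 35% active (the open-label rate of 8/23, protocol 7.6.2) and 20% sham. Here d counts all drop-outs, each with a value to carry.

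| Drop-out A/S | q_A/q_S | Missing = 0 | LOCF |
|---|---|---|---|
| 15%/15% | equal | 12.7 | 12.7 |
| 15%/15% | 20%/10% | 12.7 | 14.2 |
| 15%/15% | 35%/10% | 12.7 | 16.5 |
| 20%/10% | 35%/10% | 10.0 | 16.0 |
| 10%/20% | 35%/35% | 15.5 | 12.0 |

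The shift can be zero or favour either arm.

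**5. Can one subject matter?** In assumed tables, 20/62 against 11/62 gives chi-squared p = 0.062 and 21/62 against 11/62 gives 0.040, before adjustment. Fisher's test gives 0.096 and 0.064, so the same change does not cross 0.05 there.

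**6. Which analysis is touched.** mITT is the principal set (SAP 10.5) and requires the minimal stimulation time (protocol 12.7.2): 0.70 × 2400 = 1680 qualifying minutes, first week not counted (protocol 9.1.5). At 80 minutes on 5 days a week, a subject leaving on day 28 has 3 × 400 = 1200 and on day 35 has 1600. Only 80 minutes on all 7 days reaches 21 × 80 = 1680 by day 28. The per-protocol set excludes non-completers. LOCF therefore acts mainly in ITT, and in mITT on subjects who leave late or miss Visit 4. The SAP's own definitions of these three sets are not in the text available, so the protocol's are used.

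**The case against.** The strongest case against the point is that the rule is pre-specified and the same in both documents, the shift is about 1 point (less than one subject per arm), and most early leavers never enter the principal analysis. Non-responder imputation is also a single-imputation convention, and step 3 shows LOCF falling between it and missing at random. All of this stands, and it makes the point an improvement rather than a threat to the trial. It does not justify having one rule and no check on it.

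Several stronger readings are tempting, but the documents do not support them:
- *The SAP contradicts the protocol.* Protocol 12.9.5 prescribes LOCF in the same words. The 0-otherwise phrase in 12.2.2 is a coding definition. It is compatible with deriving status from a carried value first, so at most it needs a clarifying sentence.
- *The plan rejects LOCF for this scale.* It declines LOCF for the repeated-measures model on grounds of linearity. That reason does not reach a chi-squared or Fisher test, and a last-value analysis of HDRS-17 remains permitted.
- *Everyone who leaves after week 4 becomes a responder.* Only those whose last rating met the criterion do. For the others, LOCF and non-response agree.
- *Withdrawals for suicidal intent inflate the principal result.* mITT requires no post-randomisation exclusion criterion, and a C-SSRS yes to Q4 or Q5 is part of exclusion criterion 12. The example belongs to ITT.
- *Week-16 rates are carried forward too.* The sentence names week 8 as its example. The week-16 rates are exploratory and limited to the original active arm, and the between-visit comparisons use GEE. The open wording leaves the scope unclear but does not state this.

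**Conclusion.** The point holds in a limited form. LOCF is the only stated handling of missing week-8 response and remission. It credits leavers whose last rating met the criterion, and it differs without explanation from the missing-at-random handling of the same HDRS-17 in the primary model. Neither the denominator for subjects with no post-baseline HDRS nor a sensitivity analysis of the rule is specified.

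The size is about 1.1 active and 0.5 sham leavers of 62 per arm in ITT, or about 1 point on the treatment difference. This rests on the assumed baseline, week-8 means and drop-out timing, and on drop-out that is equal and unrelated to outcome. Under the unequal scenarios tried, the shift ran from -3.5 points (15.5 to 12.0) to +6.0 points (10.0 to 16.0). A reader might infer a bias towards the device or an inflated type I error. Neither is shown, because the direction depends on who leaves. The consequence falls mainly on the ITT consistency analysis, and in mITT on late leavers and missed Visit 4 ratings.

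**What to change.** In SAP section 7, replace LOCF for week-8 response, week-8 remission and the 7-point HDRS-17 endpoint with the following:
- Derive each endpoint from multiple imputation of HDRS-17 under the primary model's missing-at-random assumption.
- Keep all subjects of the analysis set in the denominator, including those with no post-baseline HDRS.
- Pre-specify missing = non-responder as a sensitivity analysis.
- State how the 0-otherwise coding in protocol 12.2.2 applies to a missing week-8 value, and whether any carry-forward applies beyond week 8.

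This is best settled before the treatment code is opened. SAP section 6 says that it had not been revealed when the SAP was finalised.

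The cost is SAP wording and modest programming. Reported rates may fall slightly under the non-responder analysis (31.6% against 33.4% in the active arm of step 3). Under multiple imputation they could move either way, and in that scenario they would rise.
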